3.4.10.3 Post-Operative Care and Dietary Guidelines

Subjects will be held for at least one night at West Penn Hospital and their condition monitored closely post-operatively. Prior to discharge, subjects will undergo a Barium Swallow (BaSW) to ensure there are no leaks from the procedure. Subjects will also receive careful instruction concerning their post-operative care and an at-home dietary plan will be provided and explained. This dietary plan is part of standard patient care for any stent placement procedure and recommends a soft texture with supplemental high-calorie liquid diet until the stent is removed. This diet plan is intended to prevent food-bolus obstruction while providing adequate nutritional intake. Please see VOL_011, file "006_Stent Placement Dietary Plan" for full details.

3.4.10.3.1 Management of Post-Operative Events & Food Bolus Obstruction

Due to the experimental nature of this study, adverse events could occur after a patient is discharged from West Penn Hospital. Patients will receive education related to post-operative complications such as bleeding, extreme pain, fever, and dysphagia, and will be asked to return to the hospital if such events occurs.

As part of pre-discharge dietary counseling, food bolus obstruction will be addressed. If a subject experiences a suspected food bolus obstruction or dysphagia, they will undergo an immediate endoscopic evaluation. If a food bolus obstruction is identified, it will be extracted with precision as to not disturb the esophageal stent and to protect the airway. The stent may need to be repositioned if it has migrated more than 1 cm from its original placement location. This will be done using rat-toothed forceps. The subject will be evaluated following any food bolus obstruction and/or stent repositioning to ensure no tissue damage has occurred. The subject will be re-c counseled by a staff Dietitian following bolus clearance in an effort to avoid the event from reoccurring.

3.4.11 Removal of Stent

At the Week 2 EGD, the stent will be partially collapsed for transoral removal. In order to remove the WallFlex™ Fully Covered Esophageal Stent, the Investigator will grasp the distal end of the stent using rat tooth forceps. Once the distal end is securely held, the Investigator will grasp the Teflon® coated polyester removal suture at the proximal end of the stent using rat tooth forceps and gradually apply tension (7,11,12, Please also see MISC FILES “002_Stent Removal Technique Video”). The gentle tension begins to collapse the stent; reducing the stent diameter and decreasing the contact pressure between the stent and esophageal wall. As the suture is pulled, the stent will begin to collapse, pulling away from the ECM. At 14 days post placement, the ECM is securely incorporated into the native tissue and does not provide a hindrance to stent removal. The stent will be examined for any tissue embedment and will then slowly be removed transorally in a semi-collapsed state. The 7-0 Vicryl sutures originally holding the ECM to the stent maintain 0% of their original BSR after 14 days, thereby providing no additional tether between the stent and ECM.

A note concerning stent removal: Successful removal of fully covered self-expanding metal esophageal stents such as the WallFlex™ Fully Covered Stent is supported by multiple published retrospective and animal studies (7, 9-14). The Investigators of this study have had extensive experience removing esophageal stents including removal following TEGR. The PI and Co-I have both removed stents from individuals undergoing esophagectomy to treat esophageal cancer. In prior experiences with TEGR with ECM placement, stents have been easy to remove and no stent fracturing has occurred.

3.4.11.1 Contingency Plan - Stent Removal Technique

In prior experiences with stent removal post ECM placement, the stents have been able to be removed using rat-tooth forceps as described above. There have been instances during routine clinical care that the Investigators have not been able to remove stents as described. Typically this is because the removal suture is no longer visible. In these cases, the Investigators have utilized an approach in which the stent is pulled into the stomach using retroflexion of the endoscope. In this process, the distal margin of the stent is grasped using forceps while the scope is in retroflexion and the stent is gently pulled into the stomach (grasped from below). The removal suture typically becomes visible once the stent is lowered into the stomach. At that point, the endoscopist has greater maneuverability to partially collapse of the stent using rat-toothed forceps and oral removal can be achieved.

3.4.11.2 Contingency Plan – Removal of a Fractured Stent

In previous experiences with removing esophageal stents, poor stent integrity has not been observed. While stent fracturing has not been observed, a contingency plan for coping with this possible outcome will be employed if needed. Several tools may aid in the removal of broken stent pieces. Rat tooth forceps may be used for larger pieces that do not appear to have any sharp edges that could pose risk of abrasion, laceration, or perforation of the esophagus. An EMR retrieval snare could also potentially be used for larger, smooth pieces. An EMR cap with suction could remove any small pieces. The pieces can be suctioned directly into the cap. The cap provides a protective encasement for small fragments and reduces the likelihood of esophageal damage. A Roth Net may be used for any pieces that fall into the stomach. The major benefit of the Roth Net is the protective netting that may prevent any sharp pieces from lacerating the stomach or esophagus upon removal. All extracted pieces will be reviewed outside the body to ensure no fragments remain in the Subject. The investigator will re-introduce the endoscope and carefully view the esophagus, stomach, and duodenum to further ensure no pieces remain inside the body.

3.4.11.3 Contingency Plan – Esophageal Injury

Serious esophageal injury has not been previously observed in patients who have had esophageal stents removed. Removing esophageal stents typically results in superficial injury to the mucosa and minimal bleeding can be observed. The appearance of the esophageal lining will be documented through endoscopic photographs taken at 2 weeks (stent removal), month 1, and month 3.

In the event serious esophageal injury occurs during stent removal, the following steps will be taken per standard of care measures for esophageal laceration or perforation:

- The patient is first stabilized while sedated during stent removal. Immediate surgical repair may be initiated. The patient will be fully sedated by an anesthesiologist. Debridement of any excess tissue will occur. The muscular layer is incised longitudinally along the muscle fibers above and below the perforation to reveal the entire mucosal injury. The mucosa is then closed with absorbable sutures and the muscularis layer is closed with non-absorbable sutures.

- Some patients may undergo a secondary stent placement using a fully covered plastic stent to seal the tear as opposed to surgical repair.
- The subject will be admitted so that he/she can be monitored for indications of fever, infection, mediastinitis, and other post-operative complications.
- The subject will be NPO for at least 7 days and will be placed on broad spectrum antibiotics for 7-10 days
- The patient will have a barium swallow prior to discharge to ensure no persistent leak remains
- The subject will be placed on a semi-solid diet and followed-up on a consistent basis (1 week post-op, 2 week, 6 week).

3.4.11.4 Evaluation of Esophageal Mucosa following Stent Removal

Immediately following stent removal, the esophageal mucosa will be carefully assessed endoscopically for the following indications:

- Excessive bleeding
- Perforation
- Tear
- Necrosis
- Areas of ECM removed by stent
- Excess/loose ECM
- Visible stricture

3.4.12 Adverse Events (AE)

An adverse event is defined as any untoward or unfavorable medical occurrence in a human subject, including any abnormal sign (for example, abnormal physical exam or laboratory finding), symptom, or disease, temporally (timing of) associated with the subject's participation in the research, whether or not considered related to the subject's participation in the research.

An underlying disease that was present at the time of enrollment is not reportable. However, any increase in the severity or seriousness of the underlying disease is to be reported as an adverse event.

Events meeting the definition of an AE include:

- Exacerbation of a chronic or intermittent pre-existing condition including either an increase in frequency and/or intensity of the condition.
- New conditions detected or diagnosed after investigational product administration even though it may have been present prior to the start of the study.
- Signs, symptoms, or the clinical sequelae of a suspected interaction.

The following list includes, but is not limited to, events that will be considered adverse events for this study:

- 1) stent migration,
- 2) perforation,
- 3) severe pain,
- 4) bleeding,
- 5) fever,
- 6) reflux,
- 7) aspiration and
- 8) severe stricture formation refractory to dilation

Events that do not meet the definition of an AE include:

- Medical or surgical procedure (e.g., endoscopy, appendectomy); the condition leading to the procedure is an AE.
- Situations where an untoward medical occurrence did not occur (social and/or convenience admission to a hospital).
- Anticipated day-to-day fluctuations of pre-existing disease(s) or condition(s) present or detected at the start of the study that do not worsen.
- The disease/disorder being studied or expected progression, signs, or symptoms of the disease/disorder being studied, unless more severe than expected for the subject's condition.

All adverse events will be assessed and coded in accordance with CTCAE 4.0. Adverse events will be documented through a subject specific AE log and AE CRF.

3.4.12.1 Adverse Event Relatedness

Investigators will assess the potential relationship of an adverse event to the study procedure.

Device related: An adverse event that results from the presence or performance of the devices (ECM and/or Stent) or other component of the system. For example, stent migration due to incomplete expansion.

Procedure related: An adverse event that occurs due to the study procedure. For example, perforation caused by resection or stent removal.

Whether device or procedure related, all adverse events will be classified using the FDA relatedness categories: not related, unlikely related, possibly related, related.

3.4.12.2 Observations and Complications

Investigators will determine whether an adverse event is a complication or an observation.

Complication: An adverse event resulting in death, permanent injury, or requires an invasive intervention to prevent death or permanent injury. Semi-invasive procedures (i.e. blood transfusions) will be considered a complication.

Observation: An adverse event that does not result in death, permanent injury, or requires an invasive intervention to correct.

Invasive procedures performed solely for diagnostic or surveillance purposes are excluded.

3.4.12.3 Serious Adverse Events (SAE)

A serious adverse event is defined as any adverse event temporally associated with the subject's participation in research that meets any of the following criteria:

- Results in death;
- is life-threatening (places the subject at immediate risk of death from the event as it occurred);
- requires inpatient hospitalization or prolongation of existing hospitalization;
- results in a persistent or significant disability/incapacity;
- results in a congenital anomaly/birth defect; or
- any other adverse event that, based upon appropriate medical judgment, may jeopardize the subject's health and may require medical or surgical intervention to prevent one of the other outcomes listed in this definition (examples of such events include allergic bronchospasm requiring intensive treatment in the emergency room or at home, blood dyscrasias or convulsions that do not result in inpatient hospitalization, or the development of drug dependency or drug abuse).

3.4.12.4 Unanticipated Adverse (Device) Events (UAE/UADE)

Per 21 CFR 812.3(s) "an unanticipated adverse device effect means any serious adverse effect on health or safety or any life-threatening problem or death caused by or associated with, a device, if that effect, problem, or death was not previously identified in nature, severity, or degree of incidence in the investigational plan or application, or any other unanticipated serious problem associated with a device that relates to the rights, safety, or welfare of subjects."

If an adverse event is determined to meet the definition of an unanticipated adverse event, the Principal Investigator will immediately conduct an evaluation. An unanticipated adverse device effect that represents an unreasonable risk for subject health or a product performance failure becomes apparent, immediate action will be taken and the appropriate authorities will be notified.

In the event of an unanticipated adverse device effect, which presents an unreasonable risk, for subject's health or a product performance failure becomes apparent, immediate action will be taken and the appropriate authorities will be notified.

Since these are approved devices, any UAE should also be reported to the manufacturer of the product as per user facility reporting requirements at your hospital/institution.

3.4.12.5 Adverse Events Reporting

All adverse events will be reported to the ASRI-WPAHS Institutional Review Board and FDA (as necessary) in a manner consistent with institutional and FDA guidelines (FDA guidelines cited below). In accordance with applicable policies, the investigator will report any adverse effect that is determined to meet the following criteria: *1) associated with the investigational device or, if applicable, other study treatment or diagnostic product(s); 2) a serious adverse effect; and 3) an unexpected adverse effect.*

Applicable adverse effects will be reported to the IRB as soon as possible and, in no event, later than 10 calendar days following the investigator's receipt of the respective information. Adverse effects which are *1) associated with the investigational device or, if applicable, other study treatment or diagnostic product(s); 2) fatal or life-threatening; and 3) unexpected* will be reported to the IRB within 24 hours of the investigator's receipt of the respective information.

Follow-up information to reported adverse effects will be submitted to the IRB as soon as the relevant information is available. If the results of the investigator's follow-up investigation show that an adverse effect that was initially determined to not require reporting to the IRB does, in fact, meet the requirements for reporting; the investigators will report the adverse effect to the IRB as soon as possible, but in no event later than 10 calendar days, after the determination was made.

3.4.12.5.1 FDA Guidelines

The investigators will be required to submit a report of a UAE/UADE to the IRB as soon as possible, but in no event later than 10 working days after the investigator first learns of the event (§ 812.150(a)(1)).

The sponsor investigator will conduct an evaluation of a UAE/UADE and will report the results of the evaluation to FDA, the IRBs, and participating investigators within 10 working days after notice of the effect (§§ 812.46(b), 812.150(b)(1)).

4. DATA COLLECTION

The following table lists the various intervals at which data is to be collected:

Interval	Data To Be Collected	Time of Collection
Screening/Baseline	ICF Demographics Medical history Prior medications Physical exam Pregnancy test (females) Results from the following: PET/CT Scan EUS BaSW	Prior to Treatment

	EGD with Biopsy EMR Blood Work Chest X-ray (if required) ECG (if required) PFT (if required) Questionnaires	
Treatment	TECR with ECM Placement Documented Dietary Consult	Day 0
Initial Follow-Up	BaSW	Day 1
Stent Removal	Stent Removal EGD with Biopsy EGD Photos Dilation of Stricture if present Questionnaires Vitals	Week 2
Follow-Up	EGD with Biopsy EGD Photos (months 1,3,12) Dilation of Stricture if present Questionnaires Barium Swallow x-ray test Vitals	Month 1, 3, 6, 9, 12
Anytime	Concomitant medications Adverse Event Follow-Up Adverse Event Protocol Deviation/Violation Death Termination	At Time of Occurrence, or When Notified of Event

5. STATISTICAL METHODS AND DATA ANALYSIS

This study is a feasibility study in order to assess general efficacy, collect clinical information, make observations, report adverse and serious events, and to provide the basis for possible future applications of TECR with ECM placement. The proposed sample size of 10 is not sufficient to conduct a comprehensive statistical analysis. However, we set forth efficacy and safety objectives in order to standardize our data collection points and outline specific criteria for consideration. Additionally, we have developed a statistical analysis plan that may be useful in future applications of TECR with ECM placement in the event enrollment is increased or extended to include those with T1a esophageal adenocarcinoma.

5.1 Primary Efficacy Objectives

Efficacy of the TECR with ECM placement will be assessed via two primary efficacy objectives that will assess efficacy of TECR with ECM placement at 2 weeks post-procedure through the study endpoint at 12 months. Both primary objectives will be considered in order to demonstrate overall efficacy of TECR with ECM placement.

5.1.1 *Primary Efficacy Objective 1*

To record incidence of stricture formation requiring dilation, following TECR with ECM placement. Evidence of stricture formation will be confirmed endoscopically at 2 weeks, and endoscopically and using barium swallow test at Month 1, Month 3, Month 6, Month 9, and Month 12 post procedure, and the proportion of subjects with and without stricture formation at the trial endpoints will be compared to historical data.

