2.1 Primary Objectives

2.1.1 Primary Efficacy Objectives

1. To evaluate incidence of stricture formation requiring dilation ($\geq 30\%$ luminal diameter reduction with dysphagia) following TECR with ECM placement. Evidence of stricture formation will be confirmed endoscopically at 2 weeks, and endoscopically and through barium swallow at Month 1, Month 3, Month 6, Month 9, and Month 12 post procedure, and the proportion of subjects with and without stricture formation at the trial endpoints will be compared to historical data.
2. To evaluate incidence of recurrence of BE with HGD through 12 months following TECR with ECM placement. Incidence of disease recurrence will be confirmed endoscopically with pathology confirmed biopsies at 2 weeks, Month 1, Month 3, Month 6, Month 9, and Month 12 post procedure, and the proportion of subjects with and without disease recurrence at the trial endpoints will be compared to historical data.

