5.1.1.1 Parameter of Interest

The parameter of interest is the percent of subjects with stricture formation.

5.1.2 *Primary Efficacy Objective 2*

To record incidence of recurrence of BE with HGD through 12 months following TECR with ECM placement. Incidence of disease recurrence will be confirmed endoscopically with pathology reviewed biopsies at 2 weeks, Month 1, Month 3, Month 6, Month 9, and Month 12 post procedure, and the proportion of subjects with and without disease recurrence at the trial endpoints will be compared to historical data.

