5.1.2.1 Parameter of Interest

The parameter of interest is the percent of subjects with recurrence of BE.

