5.4 Size and Duration of Trial

Ten (N=10) subjects will be enrolled in this study. Follow-up on each subject will be 12 months, except in the case of early death, losses to follow-up, or other censoring events.

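### Primary recurrence is defined two ways (BE with HGD, or any BE), and the promised historical comparisons have no named source in 5.1; if the trial is expanded, the 5.5.4 chi-square as worded tests 50% rather than the cited 41%

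*Combined protocol and SAP*

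**What the plan says.** **Recurrence.** The second primary efficacy objective in 2.1.1 reads "To evaluate incidence of recurrence of BE with HGD through 12 months following TECR with ECM placement", and 5.1.2 uses the same event. The parameter under it, in 5.1.2.1, is different: "The parameter of interest is the percent of subjects with recurrence of BE". Section 5.5.4 also counts recurrence of BE, although 5.5.1 keeps HGD in its endpoint.

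**Stricture.** The first objective in 2.1.1 is "To evaluate incidence of stricture formation requiring dilation", with the event defined as narrowing of at least 30% together with dysphagia. The parameter in 5.1.1.1 is shorter: "The parameter of interest is the percent of subjects with stricture formation". Section 5.5.1 keeps the need for dilation but leaves out dysphagia.

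**Historical comparison.** Sections 2.1.1 and 5.1.1 say that "the proportion of subjects with and without stricture formation at the trial endpoints will be compared to historical data". For recurrence, 2.1.1 and 5.1.2 say that "the proportion of subjects with and without disease recurrence at the trial endpoints will be compared to historical data". Section 5.1 gives no source, rate or interval.

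**Status of the analysis.** The opening of section 5 warns: "The proposed sample size of 10 is not sufficient to conduct a comprehensive statistical analysis". Section 5.4 allows 12 months of follow-up "except in the case of early death, losses to follow-up, or other censoring events". Section 5.5 is a possible future analysis for 30 or more subjects. Within it, 5.5.4 compares patients who did and did not have stricture by chi-square. Later in the same paragraph it gives 41% as the historical stricture rate, citing reference 19, whose title concerns cervical strictures after esophagectomy.

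**The concern.** For the trial as it stands there are two problems. First, the primary recurrence count depends on which section the analyst follows. Any BE includes BE with HGD, so the 5.1.2.1 count can only equal or exceed the count under the objective. Second, both primary efficacy results are to be set against history, but 5.1 does not say which history. A source chosen after the results are known could make the same count look good or bad.

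If the study is expanded and 5.5.4 is applied as worded, a stricture rate could be reported as significantly low because it differs from an even split, although it does not differ from the 41% that the plan cites.

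**Working it through.** The plan gives no power, target rate or margin for N=10, so there is no sample-size figure to reproduce. The checks below show how far each ambiguity can move a result.

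**1. Recurrence definition.** Input: the investigators' earlier five-patient series in section 1, where two patients had a small focus of recurrent BE and none had recurrent cancer. HGD status of the two is not given.
- As any BE: 2/5 = 40%, exact (Clopper-Pearson) 95% CI 5.3% to 85.3%.
- As BE with HGD: between 0/5 and 2/5. For 0/5 the upper limit is 1 − 0.025^(1/5) = 52.2%.

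The same five patients therefore give a point estimate anywhere from 0% to 40%.

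**2. What N=10 can show against any benchmark.** Exact 95% CIs: 0/10 is 0% to 30.8%, 1/10 is 0.3% to 44.5%, 2/10 is 2.5% to 55.6%. If 41% were used as context for stricture, only 0/10 would exclude it on the favourable side. The Wilson interval for 1/10, 1.8% to 40.4%, would also just exclude it, so the interval method needs naming.

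**3. Subjects who cannot be evaluated.** Assumption for illustration: 10 treated, 2 not evaluable, 2 events among the other 8.
- Evaluable only: 2/8 = 25.0%, CI 3.2% to 65.1%.
- Non-evaluable counted as event-free: 2/10 = 20.0%, CI 2.5% to 55.6%.
- Non-evaluable counted as events: (2+2)/10 = 40.0%, CI 12.2% to 73.8%.

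**4. Conditional on expansion: the null in 5.5.4.** Comparing the share with stricture, p, to the share without, 1 − p, in one cohort has the null p = 1 − p, that is p = 50%. Take 9 strictures in 30, with the two-sided 0.05 level of 5.5.1.
- Against 50%, expected 15 and 15: (9−15)²/15 + (21−15)²/15 = 4.8, p=0.028.
- Against 41%, expected 12.3 and 17.7: (9−12.3)²/12.3 + (21−17.7)²/17.7 = 0.885 + 0.615 = 1.50, p=0.22.
- Exact binomial against 41%: p=0.27.

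The largest count declared significantly low, and the chance of reaching it when the true rate is 41%:

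| Test at N=30 | Significantly low at | Probability if true rate is 41% |
|---|---|---|
| Chi-square as worded (50%) | 9 or fewer | 14.9% |
| Chi-square against 41% | 7 or fewer | 3.4% |
| Exact binomial against 41% | 6 or fewer | 1.3% |

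**The case against.** The strongest reply is that this is a declared feasibility study. The opening of section 5 disclaims comprehensive analysis, 5.1 speaks of recording incidence, and there is no success threshold on which a decision turns. That stands: the missing test and analysis set in 5.1 are mostly missing detail, and no significance test should be read into N=10. It does not withdraw the promised comparison, and it does not reconcile the two recurrence definitions.

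Several stronger readings are tempting but unsupported:
- *The trial's primary analysis tests 50%.* It does not. The chi-square belongs to 5.5, which applies only on expansion. Even there, expected counts of 41 and 59 per 100 are a plausible intent. The fair criticism is that the text does not link the 41% to the test.
- *The denominator might be everyone who consented.* Section 3.4.4 does enroll subjects at consent, but the events are those following the procedure and ineligible subjects do not undergo it. The live choice is between all treated subjects (5.5.1) and those with Week 2 stent removal and a valid biopsy (5.5.4).
- *The stricture parameter contradicts its objective.* Section 3.4.9.7 glosses stricture formation as 30% narrowing with dysphagia, so 5.1.1.1 is largely shorthand and needs only tidying.
- *The 41% is an improper comparator.* Section 1 names esophagectomy as the standard of care, so the rate can serve as context. The plan does not claim that it isolates the effect of the matrix.

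**Conclusion.** The point holds in two parts.

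**Active, at N=10.** The primary recurrence parameter contradicts its objective, and the choice can move an estimate as far as 0/5 versus 2/5 in the plan's own earlier series. Historical comparisons are promised for both endpoints with no source in 5.1, and recurrence has no benchmark anywhere. It is also unclear whether the comparison uses cumulative incidence or status at a visit: objective 2 runs through 12 months, while the comparison sentences refer to the trial endpoints. The difference matters most for a stricture that is dilated and resolves.

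**Conditional, at 30 or more.** Read literally, the 5.5.4 test has the wrong null for a historical comparison. If the true rate is 41%, it declares a low rate 14.9% of the time, against 3.4% or 1.3% for tests of 41%.

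This rests on the wording of 5.5.4 taken literally, on the printed title alone for the nature of the 41%, and on the assumed two non-evaluable subjects in step 3. It should be corrected, but it does not undermine a descriptive feasibility study.

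**What to change.** For the current trial:
1. Use one recurrence definition in 2.1.1, 5.1.2, 5.1.2.1 and 5.5.4, for example BE with HGD as the primary event and any BE on a separate line.
2. Name a historical source for each endpoint before results are known, or delete that comparison. If 41% is used for stricture, label it a post-esophagectomy rate given as standard-of-care context.
3. State that any comparison at N=10 is descriptive, and report the count among treated subjects with an exact (Clopper-Pearson) 95% CI.
4. Say whether each event is cumulative through Month 12 or status at Month 12. Show results among evaluable subjects and again with non-evaluable subjects counted as events, so that they are not event-free by default.
5. Minor: repeat the full stricture event of 2.1.1 (dilation needed, narrowing of at least 30%, dysphagia) in 5.1.1.1, in the comparison sentences of 2.1.1 and 5.1.1, and in 5.5.1.

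For 5.5.4, should the trial expand: replace the with-versus-without chi-square by a one-sample, two-sided exact binomial test against a stated benchmark (41%, labelled as above, if that is the one intended), or report the CI only. Do not apply a with-versus-without test to recurrence.

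The cost is wording only: follow-up biopsies are already graded for dysplasia (3.4.9.1.1), and no visits or subjects are added. The downside is a more limited historical conclusion, and possibly none for recurrence.
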